**MARS – Cash payment and counseling during
pregnancy**

MARS

Study protocol

Number of the Ethical Approval: BB 154/20
AUGUST 7, 2020

1. Background

Smoking constitutes a risk of disease regardless of the dosage. Nevertheless, smoking is common among women in childbearing age and especially among those with a lower socio-economic status. Meta-analyses have shown that psychosocial interventions for quitting smoking have positive effects on both mother and child. Further, there is evidence from international studies on the efficacy of rewards in combination with psychosocial counseling. However, there is a lack of German studies on incentives to achieve smoking cessation among pregnant women. Therefore, in our current study, we ask how rewards are most effective in supporting smoking cessation in pregnancy.

2. Objectives

The primary outcome of this pilot study is the adherence of initially smoking pregnant women to the monitoring of the smoking status up to the birth of the child / children. Secondary outcomes are (1) differences in number of cigarettes per day by self-report, (2) number of attempts to stop smoking by self-report, (3) number of attempts to stop smoking by carbon monoxide measurement. All outcome data are collected between baseline and up to pregnancy week 36.

3. Methods/ Study design

The study region is Schwerin, a city with approximately 95.000 inhabitants in Northeast of Germany. MARS is a pilot study consisting of up to three assessments for the completion of a standardized survey at three time points (baseline, pregnancy week 36 , and 8 weeks after the delivery, as well as participation in the evaluation of the smoking status twice a week using breath carbon monoxide (CO) monitor piCObaby™ Smokerlyzer (Bedfont Scientific). After an initial survey, the participating women are scheduled twice a week for counseling and evaluation of the smoking status. They will receive cash payment of 25 Euro if her CO reading does not exceed value "3" on two consecutive dates per week.

Study population

The study population consists of pregnant women who meet the following inclusion criteria:

- (1) Current pregnancy between pregnancy week 15 and 23,
- (2) Current smoking of at least one cigarette per day

Recruitment

Pregnant women will be recruited by the staff of a counseling center for pregnant women in Schwerin. A short personal screening is performed to assess the inclusion criteria. For women who meet the inclusion criteria, an initial survey is conducted and data on socio-demographic variables (age, partnership, number of children, education), current pregnancy, smoking, alcohol consumption, physical activity, fruit and vegetable consumption are collected. The participating women are scheduled twice a week for counseling and evaluation of the smoking status. They will receive cash payment of 25 Euro if their CO reading does not exceed value "3" on two consecutive dates per week. A second survey will be conducted in pregnancy week 36 and a third survey, eight weeks after the delivery.

Documentation, data storage, and data security

All participants receive a study ID at the first visit in the examination center to ensure their correct assignment over time. Data from the self-administered questionnaire and data from the breath carbon monoxide examination will be stored in a central data base. Personal data (name, address, telephone number) will not be entered in the data base. The data storage is managed according to the standards for data security and data privacy. Only the staff members of the project team have access to personal data during the study.

Data analysis

Adherence to the study protocol will be investigated using drop-out analysis. Descriptive statistics of (1) differences in number of cigarettes per day by self-report, (2) number of attempts to stop smoking by self-report, and (3) number of attempts to stop smoking by carbon monoxide measurement will be calculated. The software package STATA (version 15.1) will be used.

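### The change in cigarettes per day rests on unblinded self-report alone, and the protocol states no comparison with the CO readings scheduled in the same week

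*Protocol*

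**What the plan says.** Protocol section 2 (Objectives) makes adherence to monitoring the primary outcome and lists three secondary outcomes. The first is "differences in number of cigarettes per day by self-report". The other two count quit attempts, once from self-report and once from CO. The Data analysis section repeats the list and plans descriptive statistics for each item.

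On timing, Objectives states "All outcome data are collected between baseline and up to pregnancy week 36". Recruitment adds "A second survey will be conducted in pregnancy week 36 and a third survey, eight weeks after the delivery". The surveys inside the outcome window are therefore the baseline survey and the one at week 36.

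On entry, Study population requires "Current smoking of at least one cigarette per day", and Recruitment says "A short personal screening is performed to assess the inclusion criteria". No CO confirmation of smoking at entry is mentioned.

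On CO, section 3 says "After an initial survey, the participating women are scheduled twice a week for counseling and evaluation of the smoking status". A weekly payment of 25 Euro depends on CO readings no higher than 3. The documentation section places the self-administered questionnaire data and the CO data in one database, with a study ID for each woman.

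**The concern.** In a before-after difference with no comparison group, any shift in how women answer the question goes straight into the result. Such a shift is plausible here. The week-36 answer comes after months of counseling aimed at stopping smoking, and no blinding is described.

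The protocol pairs a self-report measure with a CO measure for quit attempts but not for cigarettes per day. The CO quit-attempt outcome does not fill that gap. It does not say whether a woman who states 0 cigarettes at week 36 had a CO above the protocol's own threshold of 3 in that week. The pilot could therefore report a fall in cigarettes per day that its own readings contradict for some women, without a reader being able to see it.

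**Working it through.** The protocol states no sample size, effect size, standard deviation or reporting error, so there is no figure to reproduce. Three things can be checked.

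**1. Is a same-week CO reading scheduled at each end?**
- Entry is at pregnancy weeks 15 to 23. Time to week 36 is 36 − 15 = 21 weeks or 36 − 23 = 13 weeks.
- At two visits a week that is 42 or 26 scheduled CO visits.
- Week 36: yes. Visits are twice weekly, and Objectives describes monitoring as continuing until the birth.
- Baseline: not stated. CO visits are scheduled after the initial survey.

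**2. What could differential misreporting do?** Let true use be constant at T. Let a be the proportional over-report at baseline (negative for under-report) and b the proportional under-report at week 36. The false fall is T(1 + a) − T(1 − b) = T(a + b). T, a and b are all assumptions; T = 10 per day is used here.

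| a (baseline) | b (week 36) | Reported baseline | Reported week 36 | False fall |
|---|---|---|---|---|
| −20% | 0 | 8 | 10 | −2 (a rise) |
| −20% | 20% | 8 | 8 | 0 |
| 0 | 20% | 10 | 8 | 2 (20%) |
| +10% | 20% | 11 | 8 | 3 (27%) |
| +20% | 20% | 12 | 8 | 4 (33%) |

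Percentages are of the reported baseline. The sign depends on a, on which the protocol gives no information.

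**3. What would a CO comparison catch?**
- A woman who states 0 but has CO above 3 is flagged.
- A woman who smokes 10 and states 8 is not flagged, because she does not claim to have stopped. Her false fall of 2 stays.
- Misreporting at baseline is untouched, because no baseline CO is stated.
- Counting flagged women as unchanged is a bound and not an estimate. Take a woman who truly went from 15 to 2 and states 0, with an accurate baseline. Her reported fall is 15 − 0 = 15, her true fall 15 − 2 = 13, and her fall under the bound 15 − 15 = 0.

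**The case against.** The strongest reply is that this rests on silence. Only the protocol is at hand, and a concordance table for a secondary outcome could sit in an SAP that is not shown. The outcome is openly labelled as self-report, a CO-based outcome stands beside it, and no test or effect claim depends on it. This limits the point: one can say that the protocol states no comparison, not that none will be made. It does not remove the point, because the protocol itself fixes the source of this outcome as self-report and lists its summary separately.

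A reader might go further and infer that the difference is biased toward a larger reduction, with entry to a cash scheme pushing the baseline answer up and payment and counseling pushing the week-36 answer down. The documents do not support that.
- Entry needs only one cigarette per day, which gives no reason to inflate a count beyond one.
- Pregnant women recruited by counseling-center staff may also under-report at baseline, which would shrink, cancel or reverse the bias.
- The payment depends on CO and not on the survey answer, and the questionnaire is self-administered. Any week-36 pressure is social expectation, and its strength is unknown.

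A further objection is that visits are scheduled and not guaranteed, so a week-36 reading may be missing for some women. That is true, and it is met by reporting how many women have a paired reading.

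**Conclusion.** The point holds in a limited form. The change in cigarettes per day is unblinded self-report without a comparison group, and the protocol states no comparison with CO readings scheduled in the same week for the same women. Differential misreporting may therefore appear as a change in smoking. Its direction and size cannot be derived from the document. The range from a rise of 2 to a fall of 4 per day illustrates sensitivity under assumed values and does not estimate the bias in this pilot. Nor would the proposed check remove errors of that kind, since it reaches only reports of no smoking at week 36.

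The consequence is modest: a descriptive secondary outcome is harder to interpret than it need be. The change is still worth making, because the data needed are already planned.

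**What to change.** Add to Data analysis:
- Pair each week-36 self-report with the CO reading or readings of that week, and state how many women have a paired reading.
- Report how many women stating 0 cigarettes have CO above 3.
- Give the change in cigarettes per day as reported and, labelled as a conservative bound only, with those discordant women counted as unchanged from baseline.
- State that CO can contradict a report of no smoking, but does not verify a daily count and does not correct misreporting at baseline, where no CO reading is stated.

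The cost is a few lines of text and a little more analysis; no new visit or measurement is needed. The downside is that the reported reduction may look smaller.

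### The primary outcome is adherence to twice-weekly CO monitoring, but the one analysis named for it does not register visits missed by women who stay in the study

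*Protocol*

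**What the plan says.** Section 2 (Objectives) defines the primary outcome as "the adherence of initially smoking pregnant women to the monitoring of the smoking status up to the birth of the child / children". The same section then says "All outcome data are collected between baseline and up to pregnancy week 36", so it gives two different end points.

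Section 3 (Study design) describes the monitoring as "participation in the evaluation of the smoking status twice a week using breath carbon monoxide (CO) monitor", and Recruitment repeats the frequency: "The participating women are scheduled twice a week for counseling and evaluation of the smoking status". Payment depends on low CO readings "on two consecutive dates per week". Women enter under the criterion "Current pregnancy between pregnancy week 15 and 23".

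Data analysis gives adherence one sentence: "Adherence to the study protocol will be investigated using drop-out analysis". The next sentence begins "Descriptive statistics of (1) differences in number of cigarettes per day by self-report" and goes on to the other two secondary outcomes. Attendance at the CO visits is not in that list and is not summarised anywhere else in the protocol.

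**The concern.** The outcome concerns a repeated behaviour: turning up for a reading twice a week over many weeks. The named analysis concerns a single event, leaving the study. A woman can remain in the study and still miss a large share of her readings, and an analysis of departures does not show this.

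The object also shifts. Objectives speaks of adherence to the monitoring, while Data analysis speaks of adherence to the whole protocol, which also includes the surveys.

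Adherence is the main result of this pilot, and payment requires two readings in the same week. Whether women come twice a week is therefore central to whether the scheme can work. If the plan is followed as written, the report could describe retention well and say nothing about attendance at the schedule.

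**Working it through.** The protocol states no sample size, expected adherence or drop-out rate, so there is no figure to reproduce. The check uses the schedule alone.

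**Inputs**
- Visits per week: 2 (Study design; Recruitment).
- Entry: pregnancy week 15 to 23 (Study population).
- End: week 36, or birth (both in Objectives). Birth at week 40 is my assumption.

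**Step 1. Scheduled visits = 2 × (end week − entry week)**
- To week 36: 2 × (36 − 23) = 26, up to 2 × (36 − 15) = 42.
- To an assumed birth at week 40: 2 × (40 − 23) = 34, up to 2 × (40 − 15) = 50.

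**Step 2. What each summary shows, to week 36**

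| Pattern | Visits attended | Share | Weeks with both readings | Drop-out in the usual sense? |
|---|---|---|---|---|
| Every visit | 26/26 to 42/42 | 100% | 13 to 21 | No |
| One visit every week | 13/26 to 21/42 | 50% | 0 | No |
| One visit every two weeks | 6/26 to 10/42 | 23% to 24% | 0 | No, if drop-out means ceasing for good |
| Every visit for the first half, then leaves | 13/26 to 21/42 | 50% | about half | Yes, halfway |

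The first three rows differ widely in attendance and are identical in a drop-out analysis. The fourth row is handled properly, provided that the time of leaving is recorded.

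The 50% does not depend on how weeks are counted. Including both end weeks adds one week, and gives 14/28 to 22/44, which is again 50%.

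**Step 3. Where the difference comes from**

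Suppose that a share d of women leaves for good at times spread evenly over follow-up, and that women attend a share a of their visits while still in. Then:
- mean share of follow-up spent in monitoring = 1 − d/2
- mean share of visits attended = a(1 − d/2)
- difference = (1 − a)(1 − d/2)

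The difference is zero when a = 1 and positive otherwise. Once the timing of drop-out is used, everything it fails to capture is intermittent missing. The protocol gives neither a nor d, so no value can be put in.

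**The case against.** The strongest reply is that outcome and method agree. An outcome that runs to birth can be read as staying in monitoring until then, and drop-out analysis suits that reading. No sentence in the protocol says that adherence means the proportion of visits attended. This stands in part: the protocol is open to both readings, so a reader who infers that the named method contradicts the outcome goes too far. But even on the persistence reading, attendance at the twice-weekly schedule goes unreported.

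A second reply is that defining drop-out, the denominator and the handling of single missed visits belongs in a statistical analysis plan, which may exist. That is fair, and the missing definition is not the point here. The protocol is not silent, though. It names a method, and a plan that kept to that method in its usual sense would carry the weakness over. A per-visit definition of drop-out would remove the difficulty, but nothing in the protocol suggests one.

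A reader might also infer that the reported figure could be wrong in either direction, with retention sometimes below attendance. That follows only if drop-out analysis is reduced to the proportion still present at the end. With the timing of leaving included, Step 3 shows that the difference cannot be negative. The protocol does not say that timing will be ignored, so the two-way claim is not supported.

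Finally, the two-readings rule governs payment and is not a criterion for adherence. That is correct. It shows why intermittent misses matter to this scheme, but it does not define the outcome.

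**Conclusion.** The concern holds in a limited form. On the usual meaning of drop-out, the only analysis named for the primary outcome cannot tell a woman who attends half of her 26 to 42 scheduled visits, one each week, from a woman who attends all of them. This rests on the protocol's schedule and entry window and on that usual meaning of the term. It needs no assumed rates.

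The protocol does not show how often visits will be missed intermittently, so the size of the effect on the reported result is unknown and none is claimed. Nor is drop-out analysis shown to be wrong: it answers one legitimate reading of the outcome and leaves the other unanswered.

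Severity is minor to moderate. The study is a descriptive pilot, the CO data are to be stored, and attendance can be derived from them at any time.

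**What to change.** - **Primary adherence measure.** For each enrolled woman, report CO visits attended divided by CO visits scheduled, counting two per week from enrolment to one stated end point, or to delivery if that comes earlier. Without the delivery clause, visits falling after an early birth would count as missed. Summarise the measure over all enrolled women.
- **End point.** Reconcile birth and week 36 in Objectives, because the denominator depends on the choice: 26 to 42 visits to week 36, or 34 to 50 if birth is assumed at week 40.
- **Drop-out.** State what counts as drop-out and keep time to drop-out as a supporting description. If staying in monitoring is what the primary outcome means, say so in Objectives and still report attendance beside it.

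The cost is small. No new measurement is needed. The CO readings already go into the study database, and the denominator follows from enrolment week, the chosen end point and the delivery date. The price is a little more derivation work and an adherence figure that may look less favourable than retention.
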